## VI. Therapeutic schedule

1. Initial dosage of administration and dosage regimen: take 2mg of sirolimus once a day since the fifth to seventh day of menstruation. After one week of medicine taking, subjects are called for an interview. If a subject has severe adverse reactions and fails to tolerate the drug, her weekly dosage can be reduced to 0.5mg, where the minimum daily dosage should be 1mg / day. If the subject still fails to tolerate the drug, she should quit; if she feel unwell but tolerable, the administration should be continued for another three months. After the three months, evaluate the condition of this subject.
2. Subsequent dosage of administration and dosage regimen: if the condition of a subject is significantly improved after taking 2mg of sirolimus once a day for three months, the initial administration should be continued. If the condition of a subject shows no significant improvement, the dosage should be changed into 2.5mg-3mg once a day. If this subject fails to tolerate the dosage, she should quit this study; if she can tolerate the dosage, this dosage regimen should be executed for three months. After that, her condition should be evaluated again.
3. Iron supplement: if hemoglobin of a subject  $\leq 10.9$  g/dL, she should receive iron supplement in accordance with the standard dosage regimen. However, the iron supplement is not regarded as a part of treatment of this study and will be recorded as a part of drug combination.
4. If the condition of a patient with a rare type of uterine fibroids (including intravenous leiomyomatosis, leiomyomatosis peritonealis disseminate and benign metastasising leiomyomas) is under control with a tolerable drug, the patient can continue this drug therapy after this six-month study.

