### 2. Evaluation during sirolimus treatment

In the first month of treatment, evaluation of adverse reactions is conducted every week. In the third and sixth months, curative effects and safety of sirolimus were assessed.

1) Evaluation of curative effects: sizes of the uterus and fibroids were measured through pelvic MRI. Blood was drawn to monitor the female hormone level and impacts of bleeding and symptoms on daily life of subjects.

2) Evaluation of safety: safety parameters (such as to enquire AE and measure laboratory values, vital signs, thickness of endometrium, abnormal uterine bleeding and sizes of follicular structure including follicle and functional ovarian cysts) are monitored periodically during the study.

3) Treatment compliance: in order to monitor compliance, subjects are asked to keep an E-diary every day. Researchers track each date of studied drug taking in accordance with E-diaries. In each interview, researchers and subjects examine the data integrity of E-diaries together.

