## X. Measures of quality control

- 1) Supervision by the project leader
- 2) Establish a standard evaluation method, unify criteria of diagnosis and effect assessment etc.
- 3) Formulate plans for monitoring and treatment of adverse reactions
- 4) All researchers receive training before this study
- 5) Assign quality controllers and develop a plan for quality control with regular inspections
- 6) Devise a follow-up plan and system

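### The dose-reduction rule for severe adverse reactions cannot be followed as written: 0.5 mg lies below the 1 mg/day minimum in the same sentence

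*Combined protocol and SAP*

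**What the plan says.** Section VI, item 1 sets a starting dose of 2 mg once daily, with an interview after one week. For a subject with severe adverse reactions who cannot tolerate the drug, "her weekly dosage can be reduced to 0.5mg, where the minimum daily dosage should be 1mg / day". Two rules follow. One covers continued intolerance: "If the subject still fails to tolerate the drug, she should quit". The other covers tolerable discomfort: "if she feel unwell but tolerable, the administration should be continued for another three months".

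Item 2 of the same section governs the three-month evaluation. Its continuation rule applies "if the condition of a subject is significantly improved after taking 2mg of sirolimus once a day for three months". Its next rule reads: "If the condition of a subject shows no significant improvement, the dosage should be changed into 2.5mg-3mg once a day". A subject who cannot take the higher dose leaves: "If this subject fails to tolerate the dosage, she should quit this study".

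Two other places bear on the point. Section VIII.2 states: "In the first month of treatment, evaluation of adverse reactions is conducted every week". Section X, item 3 lists the task "Formulate plans for monitoring and treatment of adverse reactions", without giving a dose. The flow chart announced in Section VII is not visible in this copy, so what follows concerns the text only.

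**The concern.** Item 1 holds the only dose-reduction instruction in the visible text, and it applies to the subjects who are doing worst on the drug. A clinician should be able to read the reduced dose from it, but the figure given for that dose falls below the minimum stated a few words later.

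Two things are at stake. First, clinicians who each respect the minimum may still act differently: one may go straight to 1 mg/day, another may cut once to 1.5 mg/day and stop. Second, the withdrawal rule in the next sentence takes effect after the reduction. If the reduced dose is not defined, neither is the point at which a subject has failed on it. Section V.D also lists departure from the test scheme as a ground for rejecting a subject, which is a further reason for the required dose to be readable from the text.

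**Working it through.** No sample-size or power figure is involved. The check is a unit conversion of the doses in Section VI, item 1.

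**Inputs**
- Starting dose: 2 mg/day, so 2 × 7 = 14 mg/week.
- Minimum dose: 1 mg/day, so 1 × 7 = 7 mg/week.
- Reduced dose as printed: 0.5 mg, labelled weekly.

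**Can the printed figure meet the minimum?**

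| Reading of the 0.5 mg figure | Daily dose | Compared with the 1 mg/day minimum |
|---|---|---|
| Reduced *to* 0.5 mg per week | 0.5 / 7 = 0.07 mg/day | 7 / 0.5 = 14 times too low |
| Reduced *to* 0.5 mg per day | 0.5 mg/day | 0.5 / 1 = 50% of the minimum |
| Daily dose reduced *by* 0.5 mg each week | 2.0 − 0.5 = 1.5, then 1.5 − 0.5 = 1.0 mg/day | Reaches the minimum exactly in 2 steps |

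Both readings that keep the printed *to* break the minimum. The third satisfies it. It uses the same 0.5 mg figure, gives the word *weekly* a sensible role as the interval between steps, and makes a first cut of 0.5 / 2 = 25%. It also fits the weekly adverse-reaction checks that Section VIII.2 schedules for the first month, since two weekly steps can be completed within that month. It is therefore the probable intent. To reach it, however, a reader must change *to* into *by* and take *weekly* as describing the interval instead of the dose.

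**Does any other section settle it?** Section VIII.2 gives the timing of the checks but no dose step. Section X, item 3 calls for plans but gives no dose. Section V.C covers leaving the study, not reducing the dose. None of them corrects the sentence.

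**Consequence for the withdrawal rule.** Under the probable intent there are two reduced doses, 1.5 and 1.0 mg/day. The withdrawal sentence does not say which of them must have failed. A subject still unwell at 1.5 mg/day could be withdrawn at once or stepped down to 1.0 mg/day first, and the text allows either.

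**The case against.** The strongest reply is that this is a slip of language with an evident repair. The English is rough throughout, one stepwise reading fits every figure in the sentence, and the trial is run by a single department. The minimum confines any compliant reduced dose to between 1 and 2 mg/day. The reduction is worded as permitted, not required. Section V.C, items 3 and 4 allow withdrawal on safety grounds in any case. Both literal readings give a subject with severe reactions less drug, not more, so no overdose follows from item 1. A subject who cannot tolerate 1 mg/day would leave under any reading that respects the minimum. The unseen flow chart may also show the right steps.

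Most of this stands, and it limits the severity. It does not make the sentence usable: the step size and the dose at which withdrawal applies still have to be guessed. If the flow chart shows a correct path, the text would conflict with it and would still need correcting.

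A reader might also infer that item 2 sends subjects who could not tolerate 2 mg/day up to 2.5–3 mg/day, which is 25–50% higher (2.5 / 2 = 1.25; 3 / 2 = 1.50). The text does not support that as a finding. The escalation sentence reads more naturally as the other half of the preceding condition, which concerns subjects who have taken 2 mg daily for three months. On that reading nobody intolerant of 2 mg is escalated, and what remains is that item 2 gives no explicit three-month rule for subjects on a reduced dose. The documents do not say how many there would be, and there may be none.

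**Conclusion.** Section VI, item 1 is wrong as written. Its reduced dose is 0.07 mg/day if weekly or 0.5 mg/day if daily, against a minimum of 1 mg/day in the same sentence, so the rule cannot be followed literally. The dose at which the withdrawal rule bites (1.5 or 1.0 mg/day) is consequently unclear. The contradiction itself rests on arithmetic alone. The stepwise intent is an inference from the starting dose, the minimum and the weekly checks, and needs the investigators' confirmation.

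Severity is moderate. This is an operative safety-dosing rule for an off-label use, which makes it more than a clerical matter, but the error is a probable wording or translation slip and the stated minimum bounds its effect. The documents do not support a claim that subjects would be overdosed under item 1 or that the study results would change. The gap in item 2 is a matter for optional clarification and forms no part of this conclusion.

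**What to change.** Ask the investigators to confirm the intended reduction, check it against the Section VII flow chart if that shows a dose path, and then reword item 1, for example:

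*The daily dose may be reduced by 0.5 mg at weekly intervals (2.0 to 1.5 to 1.0 mg/day), to no less than 1 mg/day; a subject who does not tolerate 1 mg/day should quit.*

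This keeps the 2 mg start, the 0.5 mg figure, the weekly interval and the 1 mg/day minimum, and it settles when the withdrawal rule applies.

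Optionally, add one sentence to item 2 stating that escalation to 2.5–3 mg/day applies only to subjects who tolerated 2 mg/day. How to manage dose-reduced subjects who have not improved at three months is a clinical decision for the investigators to make and record.

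The cost is one reworded sentence and, if wanted, one added sentence. No visits, tests, data fields, analyses or subjects are added.

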#### C. Exit criteria

1. A subject suffers from an anaphylactic reaction

2. A patient asks to quit the study because of one's own will or the request of her legal representative. A subject can refuse to follow a further step of this study at any time during the study without a reason. Consequently, the subject won't be affected negatively.

3. A subject is asked to quit this study in some condition (such as obvious poor compliance and security problems)

4. Other conditions leading to termination of this study. For example, researchers think the

continuation of this study may impair health of subjects.

[figure not shown]

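### The month-3 dose increase in VI.2 depends on lack of improvement alone: a non-improver with toxicity below the exit level has no required safety review first and no option to hold her dose

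*Combined protocol and SAP*

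**What the plan says.** Section VI, item 1 starts patients on 2 mg of sirolimus daily, with an interview after one week. A patient with severe reactions that she cannot tolerate may be reduced, to no less than 1 mg a day, and leaves if she still cannot tolerate the drug. For milder trouble the rule is "if she feel unwell but tolerable, the administration should be continued for another three months", followed by an evaluation.

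Item 2 then gives two branches. A patient who is "significantly improved after taking 2mg of sirolimus once a day for three months" stays on the initial regimen. For the other branch: "If the condition of a subject shows no significant improvement, the dosage should be changed into 2.5mg-3mg once a day". Tolerance enters only after that step: "If this subject fails to tolerate the dosage, she should quit this study"; otherwise the higher dose runs for three months.

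On monitoring, section VIII.2 says "In the first month of treatment, evaluation of adverse reactions is conducted every week" and "In the third and sixth months, curative effects and safety of sirolimus were assessed". It lists adverse events, laboratory values and vital signs among the safety parameters, monitored periodically.

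On leaving or declining, section V.C item 2 says "A subject can refuse to follow a further step of this study at any time during the study without a reason". Item 3 says "A subject is asked to quit this study in some condition (such as obvious poor compliance and security problems", and item 4 allows termination where researchers think continuing may harm subjects.

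**The concern.** By month 3 the investigator should have efficacy and safety findings from the same assessment, yet the written dosing rule uses only the first. A patient who is not improving and has, for example, a newly raised liver enzyme or a lingering adverse reaction falls into the escalation branch like any other non-improver.

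An investigator who sensibly keeps her at 2 mg departs from item 2 as written. Section V.D item 1 lists breach of the trial scheme as a ground for rejection, so a prudent hold could be read as a violation. What is at stake is the safety of individual patients, for a drug that section I says has not yet been used in uterine fibroids and whose safety there still has to be shown.

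**Working it through.** The documents give no figure to reproduce, so the check is mainly a reading of the provisions together.

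**1. Size of the step.** From section VI: starting dose 2 mg/day, escalated dose 2.5-3 mg/day. 2.5 / 2 = 1.25 and 3 / 2 = 1.50, an increase of 25-50%.

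**2. What each provision does for a month-3 non-improver.**

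| Provision | Before the increase? | Makes safety results a condition of the increase? | Lets her hold her dose? |
|---|---|---|---|
| VI.1, one-week interview and reduction | Yes, but early in treatment | No | No; it concerns the starting dose |
| VI.2, improved branch | Month 3 | No | Only if significantly improved |
| VI.2, non-improved branch | Month 3 | No | No |
| VI.2, tolerance sentence | No, after it; undated | No | No; she quits or continues at the higher dose |
| VIII.2, safety assessment | Month 3 | Not linked to dose | No |
| V.C item 2, refusal | Any time | No | Not stated; can be read as declining the step without quitting |
| V.C items 3 and 4 | Any time | Yes, in effect, for problems serious enough to end participation | No; they lead to exit |
| X item 3 and XIV, adverse-reaction plans and expert supervision | General | No dosing rule given | Not stated |

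The readable text therefore has one stated condition for the increase, no statement that the month-3 safety assessment feeds into it, and no express provision for a non-improver to stay at 2 mg pending review.

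**3. What is left after the existing protections.** Among month-3 non-improvers, set aside those whose safety problem meets exit item 3 or 4 and those who decline the step themselves. That leaves patients with a new or unresolved reaction or abnormality below the exit level. VI.1 deliberately carries unwell but tolerating patients forward, so such patients are foreseeable. The group's size would need a non-improvement rate and a rate of abnormal findings. The documents give neither.

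**4. Patients already reduced.** The first sentence of VI.2 refers to patients who took 2 mg; the non-improvement sentence says only a subject. It is unclear whether someone reduced under VI.1 is included. If she were, a patient at the 1 mg floor would go to 2.5 / 1 = 2.5 or 3 / 1 = 3 times her current dose. This shows why the ambiguity should be removed; the plan does not say that this would happen.

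**The case against.** The strongest reply has four parts.

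*Safety exits apply before any increase.* Following the protocol means following V.C as well as VI.2, and items 3 and 4 operate at month 3. This stands, and it removes serious toxicity from the point. A reader might infer that a seriously ill patient must be escalated, or that anyone is compelled to take the higher dose. The documents do not support either: withdrawal is available, and the refusal sentence can be read as declining the step while remaining in the study. It does not, however, state what dose she then takes.

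*Condition may include safety.* V.A item 3 uses the word for overall health, judged partly from laboratory tests, and VI.1 has the patient's condition evaluated at three months. This is a fair textual point. But VI.2 turns the word into a choice between improved and not improved, and worse laboratory results would hardly count as a reason to raise the dose. Read broadly, the rule becomes odd rather than safe.

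*The flow chart is not shown.* A safety branch may be drawn there or in the other missing figures. This cannot be excluded, so the point is confined to the readable text and does not say that the plan as a whole lacks a check.

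*Monitoring is closer than the calendar suggests.* A reader might count two months from the end of the weekly checks to the decision, and three months on to the month-6 assessment, and call that an unmonitored gap. The documents do not support this. Safety is assessed in month 3 itself, periodic monitoring continues, and VI.2 has its own tolerance check after the increase, although undated. Those intervals are not used here as a measure of anything.

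**Conclusion.** The point holds in a limited form. On the readable text, VI.2 moves month-3 non-improvers to 1.25-1.5 times their dose without requiring the same month's safety results to be considered and without offering a hold. The exposed group is non-improvers with toxicity that is new or unresolved but below the exit criteria. It is probably small, but its size cannot be calculated from the documents. VI.2 is separately unclear for patients reduced below 2 mg.

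This rests on two assumptions: that the missing figures contain no such condition, and that VI.2 means improvement of disease when it speaks of condition. A reader might go further and infer bias in the efficacy results or a threat to the trial's conclusions; nothing in the documents shows that, and none is claimed. It is a low-cost safety clarification for the sponsor to consider. Confidence is medium, mainly because the flow chart cannot be seen.

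**What to change.** Amend VI.2 so that the dose rises to 2.5-3 mg only if both conditions are met:

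- there is no significant improvement; and
- the month-3 adverse events and laboratory values collected under VIII.2 have been reviewed and show no clinically significant abnormality and no unresolved significant adverse reaction.

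Otherwise the current dose is held or reduced, and the patient may stay in the study.

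For liver and kidney values, the V.A item 8 limits can be the reference: AST and ALT 2.5 times the upper limit of normal, bilirubin and creatinine 1.5 times. They are entry limits and do not cover blood count or blood fat, so those need investigator judgement or limits set in advance. Add a sentence that patients reduced below 2 mg under VI.1 do not go directly to 2.5-3 mg. Record the review and the dose decision on the case report form. If the flow chart shows the dose decision, align it.

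No new visit is needed, because safety is already assessed in month 3. VIII.2 speaks only of laboratory values, so it would help to name there the blood count, hepatic and renal function and blood fat tests listed in VIII.1, and the sponsor must agree any limits. The price is a short wait for results before some dose changes and slightly less experience at 2.5-3 mg.

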## III. Research content

1. Symptom control rates after medication for 3 and 6 months
2. Recurrence rates of symptoms after 12 months of drug withdrawal
3. Evaluation of safety and side effects of the drug

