## IV. Research design

1. This study is a non-random open-label clinic trial carried out by the department of gynaecology and obstetrics, Peking Union Medical College Hospital.
2. All patients who accorded with inclusion criteria and signed informed consents received sirolimus treatment for at least three months. After drug withdrawal, there patients were followed up for at least one year.
3. There should be at least 25 patients included in this study without an upper limit of included patients.

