### 3. Evaluation after treatment

Evaluation of curative effects and safety is conducted at the end of the drug therapy, six and twelve months after the treatment, where the evaluation content is the same as that before the trail.

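### Stopping sirolimus for intolerance or safety is written as leaving the study, which conflicts with the one-year post-withdrawal follow-up planned without exception for such patients

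*Combined protocol and SAP*

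**What the plan says.** All references are to the combined protocol and SAP.

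**Rules that end participation**
- Section VI item 2, intolerance of the raised dose: "If this subject fails to tolerate the dosage, she should quit this study".
- Section VI item 1, intolerance that persists after the reduction step: "If the subject still fails to tolerate the drug, she should quit". The sentence does not say whether she quits the drug or the study.
- Section V.C, Exit criteria: item 1 lists an anaphylactic reaction. Item 3 reads "A subject is asked to quit this study in some condition (such as obvious poor compliance and security problems".

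**Rules that require follow-up**
- Section IV item 2 describes patients who "received sirolimus treatment for at least three months" and continues: "After drug withdrawal, there patients were followed up for at least one year".
- Section VIII.3: "Evaluation of curative effects and safety is conducted at the end of the drug therapy, six and twelve months after the treatment". The content repeats the pre-treatment assessments, which under VIII.1 include blood count, liver and kidney function, lipids and pelvic MRI.
- Section III item 2 names an outcome that needs this follow-up: "Recurrence rates of symptoms after 12 months of drug withdrawal".

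Neither IV nor VIII.3 makes an exception for patients who stop for intolerance. Section VIII.2 says that safety parameters "are monitored periodically during the study", which ties monitoring to being in the study.

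**The concern.** Stopping the drug and leaving the study are treated as one event. For a patient who stops because of toxicity, one part of the plan sends her out and another expects her back at 6 and 12 months.

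Safety is one of the two objectives in section II, and section IX.2 item 4 calls for a judgement on whether each adverse event is related to the drug. With no control group, the course of an event or laboratory change after stopping is among the more useful evidence for that judgement. If the exit rule is followed as written, that evidence is missing mainly in the patients whose reactions ended treatment. The post-treatment safety summary would then describe mostly those who tolerated the drug. Twelve-month recurrence data could be thinned in the same selective way.

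**Working it through.** The plan gives no intolerance rate, dropout allowance or derivation of its sample size, so there is no figure to reproduce. The check is mainly a comparison of texts.

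**Step 1. Each group of stoppers against each follow-up rule**

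| Patients | What the exit rule says | Covered by IV item 2? | Covered by VIII.3? | Result |
|---|---|---|---|---|
| Intolerant of the raised dose (VI item 2) | Leave the study, in words | Yes: already three months on drug | Yes, no exemption | Direct conflict |
| Still intolerant after reduction (VI item 1) | Quit; object not stated | Possibly not, if stopped before three months | Yes, no exemption | Unclear |
| Anaphylaxis or safety problem (V.C items 1 and 3) | Study exit, by heading (item 1) or in words (item 3) | Depends on time on drug | Yes, no exemption | Conflict with VIII.3; with IV if three months were reached |

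**Step 2. Is quitting only loose wording for stopping the drug?** V.C item 2 uses the same expression for a patient who withdraws of her own will, which is plainly leaving the study. V.C item 3 and VI item 2 use it again. Nothing in the text separates the two events or says that patients who quit are still followed.

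**Step 3. Size, for illustration only**

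Inputs: N = 25, the minimum in section IV item 3; intolerance rate p = 5%, 10% or 20%, an assumption.

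Expected number leaving = 25p. Chance of at least one = 1 − (1 − p)^25.

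| p | 25p | Chance of at least one |
|---|---|---|
| 5% | 1.25 | 1 − 0.95^25 = 72% |
| 10% | 2.5 | 1 − 0.90^25 = 93% |
| 20% | 5 | 1 − 0.80^25 = 99.6% |

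*Recurrence.* If d of 25 patients have no 12-month record, the rate over all 25 lies in a band of width d/25 between best and worst case: 4 points for d = 1, 12 for d = 3, 20 for d = 5. For example, 4 recurrences in 20 followed patients give 4/25 = 16% at best and 9/25 = 36% at worst.

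*Late safety.* With no adverse event seen at the post-treatment visits in n followed patients, the upper exact 95% limit is 1 − 0.025^(1/n). That is 13.7% for n = 25 and 16.8% for n = 20. If all 5 unfollowed patients had such an event, the proportion would be 5/25 = 20%, above the 16.8% limit calculated from those followed. This is an extreme case, but it shows that an interval from the tolerant patients alone need not cover the whole group.

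**The case against.** **The loss comes from literal wording plus silence.** No passage states that follow-up ends for these patients. VI item 4 speaks of the study as lasting six months, so the word may sometimes mean the treatment phase, and VIII.3 could be read as still covering everyone who took the drug. The section VII flow chart is not in the text available here and may show how stoppers are handled. This stands as a limit on certainty. It does not remove the conflict, because staff could follow either text.

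**Three stronger readings are tempting but unsupported.**
- A reader might infer that the patients with the worst toxicity are the ones lost. The explicit wording sits in VI item 2, which sets no severity threshold. Severe reactions appear in item 1, where what she quits is not stated.
- A reader might infer that every post-treatment evaluation is lost for every such patient. The text does not show this. The end-of-therapy evaluation falls when the drug stops and might well be done.
- A reader might infer that VI items 1 and 2 contradict each other, since one has a reduction step first and the other does not. They cover different situations, the starting dose and a later increase, so there is no contradiction.

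**The scheduled visits alone add little on when an event resolved.** After end of therapy the next is at six months, and the VIII.1 list has no explicit adverse-event enquiry. IX.2 item 3 also confines its summary to events on medication. This is fair, and it is why the outcome and end date need recording separately. The causality judgement in IX.2 item 4 carries no such time limit.

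**Recurrence may be less affected than the bounds suggest.** Patients reach the raised dose because they had not improved significantly. If recurrence is counted only among patients whose symptoms were controlled, some of them would not enter it. The plan does not define that denominator, so the bounds apply only if all 25 count.

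**Section X plans for monitoring adverse reactions and for a follow-up system.** These are general statements and do not say who stays in follow-up.

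**Conclusion.** The concern holds as a conflict between provisions. Section VI item 2 and the safety grounds in V.C send patients out of the study, while IV item 2 and VIII.3 plan post-withdrawal follow-up with no exemption for them. It is clearest for intolerance of the raised dose and only an ambiguity for VI item 1. Followed literally, the exit rules selectively remove off-drug safety data, and possibly 12-month recurrence data, from patients whose toxicity ended treatment.

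The number affected is unknown. About 1 to 5 of 25 rests on an assumed rate of 5% to 20% and on the minimum enrolment. With so few patients and no control group, even that many matters for a trial with safety as an objective. The change should be made. Confidence is medium, because the intended meaning of quitting is not stated.

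**What to change.** Reconcile V.C items 1 and 3 and VI items 1 and 2 with IV item 2 and VIII.3:

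1. Define end of treatment and end of study participation as separate events, and say which one each use of quitting means.
2. State that a patient who stops sirolimus for intolerance or a safety reason stays in follow-up for the VIII.3 evaluations at end of therapy, 6 and 12 months unless she withdraws consent.
3. Record the outcome and end date of the adverse event that ended treatment.

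Changing section VI alone would leave the same problem in the Exit criteria. No change to any dose or to the rules for stopping the drug is proposed.

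Cost: an amendment and a few more visits by retained patients, including the pelvic MRI that VIII.3 already schedules for everyone. Because the visits exist in the plan, no new schedule is needed.
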